In 2006 Chanan-Khan et al published the results of a phase II trial with lenalidomide in relapsed or refractory 8-cell CLL/SLL patients. Lenalidomide was administered orally at 25 mg on days 1 through 21 of a 28-day cycle. Patients were to continue treatment until disease progression, unacceptable toxicity, or complete remission. Rituximab was added to lenalidomide on disease progression. The overall response rate was 47%, with 9% of the patients attaining a complete remission. Fatigue, thrombocytopenia, and neutropenia were the most common adverse effects noted in 83%, 78%, and 78% of the patients, respectively.

NCT00267059 study investigated the activity of lenalidomide in patients CLL/SLL. Lenalidomide was given at 10 mg daily with dose escalation up to 25 mg daily. Three patients (7%) achieved a complete response (CR), one a nodular partial remission, and 10 patients a PR, for OR rate of 32%. The most common toxicity was myelosuppression, and the median daily dose of lenalidomide tolerated was 10 mg¹⁴

Chen and collaborators conducted a trial with lenalidomide in untreated patients as single-agent. Using a starting dose of lenalidomide 10 mg/d for 21 days of a 28-day cycle and weekly 5-mg dose escalations to a target of 25 mg, they encountered severe toxicities (tumor lysis, fatal sepsis) in the first two patients enrolled. The study was halted and the protocol amended to a more conservative regimen: starting dose of lenalidomide 2.5 mg with monthly escalations to a target dose of 10 mg, and extended tumor lysis prophylaxis and monitoring. Twenty-five patients were enrolled on the amended protocol. No further tumor lysis events were reported. Tumor flare was common (88%) but mild. Grade 3 to 4 neutropenia occurred in 72% of patients, with only five episodes of febrile neutropenia. The overall response rate was 56% (no complete responses)¹⁵.

Lenalidomide in combination with Rituximab (NCT00759603) (Phase II)

In a multicenter phase II study of the CLL Research Consortium, previously untreated patients with CLL/SLL (69 patients) were treated with lenalidomide (initial dose of 2.5 mg/d, with dose escalation up to 10 mg/d; given 21 days of a 28-day cycle) combined with rituximab (dose escalated to 375 mg/m² cycle 1; 375 mg/m² weekly for 4 weeks in

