cycle 2, then on day 1 for cycles 3-7) (James et al. abst Blood 2011; 118:3489-3498). Patients in this trial were stratified by age group (age < or = 65 years). Only 59% of the older patient group completed the planned 7 cycles of therapy compared with 90% of patients younger than 65 years. Tumor flare reactions occurred in 71% of patients, but were grade 1 or 2 in nearly all cases. The most common grade 3 or 4 toxicity was neutropenia, which was reported in 49% of patients. Neutropenic fever occurred in 4 patients (6%). Among evaluable patients, the ORR in those younger than 65 years was 94% (CR in 20%) and the ORR in older patients was 77% (CR in 9%).

NCT00759603 is a single center, phase II trial for previously treated patients. Rituximab was administered intravenously on days 1, 8, 15, and 22 during cycle one and once every 4 weeks on day 1 for cycle two to 12. Lenalidomide was started on day 9 of cycle one at 10 mg per day and administered continuously. Treatment duration was planned 12 cycles but could continue lenalidomide indefinitely beyond 12 cycles if there was a significant clinical benefit, such as ongoing partial or complete response.

The OR was 66%, including 12% complete responses and 12% nodular partial remissions. Time to treatment failure was 17.4 months. Median OS has not been reached; estimated survival at 36 months is 71%. The most common grade 3 or 4 toxicity was neutropenia (73% of patients). Fourteen patients (24%) experienced a grade 3 to 4 infection and febrile episode. There was one episode of grade 3 tumor lysis; one patient experienced renal failure during the first cycle of therapy, and one venous thromboembolic event occurred during the study ¹⁶.

STUDY RATIONALE

Monoclonal antibody therapy has been found to potentiate the activity of chemotherapeutic agents. There is synergistic activity between rituximab and lenalidomide against CLL/SLL and non-Hodgkin lymphoma *in vitro* ¹¹. Furthermore, the results of our phase II trial of lenalidomide in combination with rituximab in relapsed or refractory CLL/SLL support the clinical activity of this combination ¹⁶.

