10. STATISTICAL CONSIDERATIONS

DETERMINATION OF SAMPLE SIZE

The patient sample size will be 30 patients and the Bayesian method of Thall, Simon and Estey²¹ will be employed to perform interim futility and safety monitoring.

PLANNED EFFICACY EVALUATIONS

The primary efficacy endpoint is overall response, defined as CR or PR. The secondary endpoints will be safety of the combination, response according to prognostic markers at diagnosis, time to next treatment and overall survival. Response to treatment will be assessed according to NCI-WG 2008 working group criteria at 3, 6 months from the beginning of therapy and every 6 months thereafter.

PRIMARY EFFICACY VARIABLES

Overall response, defined as CR or PR.

SECONDARY EFFICACY VARIABLES

The secondary endpoints will be safety of the combination, response according to prognostic markers at diagnosis, time to next treatment and overall survival.

METHOD OF ANALYSIS

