We will monitor futility and safety of the treatment combination using a Bayesian design by Thall, Simon and Estey, in cohort size of 10. Specifically, assuming a beta (0.8, 1.2) prior for the overall response (OR) rate, we will stop trial if $\text{Prob}\{p(\text{OR}) > 0.40 \text{ data}\} < 0.05$, where $p(\text{OR})$ is the probability of overall response. That is, if at any time during the trial we determine that there is less than 5% chance that the overall response rate is at least 40%, we will stop the trial. For futility monitoring purpose, we will assess patients' OR rate at 3 months post treatment, and at each planned cohort (i.e., 10, 20, 30, etc.) for interim look, if there is not enough number of responders (such as 1 or fewer out of the first 10, 4 or fewer out of the first 20, etc.) we will temporarily suspend accrual until all patients in the current cohort has been fully evaluated. Similarly, we will stop the trial if $\text{Prob}\{p(\text{TOX}) > 0.50 \text{ data}\} > 0.95$, where $p(\text{TOX})$ is the probability of grade 3 or higher non-hematological toxicity and a beta(1, 1) prior was used for toxicity rate. That is, if at any time during the trial we determine that there is more than 95% chance that the toxicity rate is at least 50%, we will stop the trial due to safety concern. The corresponding stopping boundaries for futility and safety are shown in Tables 7 and 8 respectively. The operating characteristics of the design are illustrated in Table 9. Multc Lean Desktop (v2.1.0) was used for generating the stopping boundaries and the OC table.

If the trial did not stop due to either futility or toxicity, then with a total sample size of 30, the 95% credible interval for the overall response rate will be (0.24, 0.57), assuming an OR rate of 0.40 and a beta(0.8, 1.2) prior.

The proportion of patients achieving OR and its 95% credible interval will be presented. In addition, we will compute the posterior probability of OR rate being greater than 40%. Similar methods will be used to analyze the toxicity data. Univariate and multivariable logistic regression models will be fit to assess the association between OR and prognostic biomarkers. The time-to-event outcomes (such as time to next treatment or overall survival) will be estimated using the Kaplan-Meier method.

Table 7. Interim futility stopping boundaries in cohort size of 10.

Number of Patients Evaluated	Stop the trial if \leq OR Observed
10	1
20	4
30	7

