Table 8. Interim toxicity stopping boundaries in cohort size of 10.

Among These Number of Patients	Stop the trial if >/= Toxicity Observed
10	8
20	14
30	20
-	-

Table 9 The operating characteristics of futility and toxicity monitoring.

True OR rate	True Toxicity Rate	Prob (stop early)	Average number of patients
0.3	0.3	0.28	25.6
0.3	0.5	0.35	24.5
0.3	0.7	0.75	17.8
0.4	0.3	0.08	28.7
0.4	0.5	0.16	27.4
0.4	0.7	0.68	19.1
0.5	0.3	0.02	29.7
0.5	0.5	0.10	28.3
0.5	0.7	0.65	19.6

In addition, we will monitor the grade 4 and grade 5 non-hematological toxicities separately, throughout the study and in cohort size of 10. Specifically, the trial will be stopped if $\text{Prob}\{p(\text{TOX4}) > 0.25 | \text{data}\} > 0.95$ or $\text{Prob}\{p(\text{TOX5}) > 0.10 | \text{data}\} > 0.95$, where $p(\text{TOX4})$ and $p(\text{TOX5})$ are the probabilities of grade 4 and grade 5 non-hematological toxicities, respectively. A beta(0.5, 1.5) prior is assumed for $p(\text{TOX4})$ and a beta(0.2, 1.8) prior is assumed $p(\text{TOX5})$. Based on these stopping criteria, the trial will be stopped early if $[\#\text{patients with grade 4 toxicities}] / [\#\text{patients evaluated}] \geq 6/10, 9/20, 12/30$ OR $[\#\text{patients with grade 5 toxicities}] / [\#\text{patients evaluated}] \geq 4/10, 5/20, 7/30$.

This protocol will use PDMS and CORE as database repositories

REPORTING OF ADVERSE EVENTS ASSESSMENT OF SAFETY

Safety assessments will consist of monitoring and reporting AEs and SAEs that are considered related to obinutuzumab or/and lenalidomide, all events of death, and any study specific issue of concern.

Adverse Events

An AE is any unfavorable and unintended sign, temporarily associated with the use of an

investigational medicinal product (IMP) or other protocol- imposed intervention , regardless of attribution.

Serious Adverse Event Reporting for MD Anderson- Sponsored IND Protocols

An adverse event or suspected adverse reaction is considered “serious” if, in the view of either the investigator or the sponsor, it results in any of the following outcomes:

Death

A life-threatening adverse drug experience – any adverse experience that places the patient, in the view of the initial reporter, at immediate risk of death from the adverse experience as it occurred. It does not include an adverse experience that, had it occurred in a more severe form, might have caused death.

Inpatient hospitalization or prolongation of existing hospitalization

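### The grade 5 stopping rule counts only non-hematological toxicity, so a treatment-related death classed as hematological enters no stopping rule, and the plan does not define the class

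*Combined protocol and SAP*

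**What the plan says.** Section 10, Method of Analysis, sets three toxicity rules, each looked at after 10, 20 and 30 patients.

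- **Main rule.** p(TOX) is the "probability of grade 3 or higher non-hematological toxicity". The trial stops if the posterior probability that this exceeds 0.50 is above 0.95 (Table 8).
- **Added rules, after Table 9.** The plan adds that "we will monitor the grade 4 and grade 5 non-hematological toxicities separately, throughout the study and in cohort size of 10". p(TOX4) and p(TOX5) "are the probabilities of grade 4 and grade 5 non-hematological toxicities, respectively". The limits are 0.25 and 0.10, again with a 0.95 cutoff. The grade 5 prior is beta(0.2, 1.8), and its boundaries are 4/10, 5/20 and 7/30.

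The sentence listing the grade 4 and grade 5 boundaries drops the word non-hematological. It applies the criteria just defined, however, so the restriction carries over.

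The only other numerical rule is futility on overall response. Section 10 does not say which events are hematological. The nearest text is Table 2 in Section 6 (platelets, hemoglobin and neutrophil count), which is given for dose modification. Appendix 3 names CTCAE version 4.0 for grading. Under Deaths, the event that caused or contributed to the death is to be recorded as one medical concept.

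**The concern.** Leaving non-fatal cytopenia out of the lower-grade rules makes sense. In the cited study of lenalidomide plus rituximab in previously treated patients, "The most common grade 3 or 4 toxicity was neutropenia (73% of patients", and the cited single-agent study in untreated patients reports 72%. Rates like these would swamp a 50% limit on grade 3 or higher events.

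That reason does not reach grade 5. A death is not a common, tolerated event to be kept out of the count, and the plan gives no reason why the organ class of its cause should matter. Because the class is undefined, two identical deaths could be treated differently. If the recorded concept is sepsis or haemorrhage, the death counts. If it is febrile neutropenia or thrombocytopenia, it may not. At stake is whether the formal fatal-toxicity boundary responds to all the deaths it appears meant to limit.

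**Working it through.** **Inputs from Section 10.** Prior beta(0.2, 1.8); limit 0.10; cutoff 0.95; looks at 10, 20 and 30; boundaries 4, 5 and 7.

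**Step 1: reproduce the stated boundaries.** With x counted deaths among n patients, the posterior is Beta(0.2 + x, 1.8 + n − x). The boundary is the smallest x for which Prob(p > 0.10) exceeds 0.95.

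| n | One below boundary | At boundary |
|---|---|---|
| 10 | x = 3: 0.933 | x = 4: 0.987 |
| 20 | x = 4: 0.875 | x = 5: 0.959 |
| 30 | x = 6: 0.931 | x = 7: 0.975 |

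These match 4/10, 5/20 and 7/30, so there is no arithmetic error.

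**Step 2: what the class of one death does.** Suppose four of the first ten patients die of treatment-related causes and one death is classed hematological. The rule sees 3/10, the posterior is 0.933, and the trial continues. If all four count, the posterior is 0.987 and it stops. If all four are classed hematological, the rule sees 0/10 and the posterior is 0.039.

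**Step 3: chance of stopping by 20 patients.** Let q be the true treatment-related death rate and h the share classed hematological. The counted rate is p = q(1 − h). With X deaths counted in the first ten patients and Y in the second ten, both Binomial(10, p):

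P(stop by 20) = P(X ≥ 4) + Σ (k = 0 to 3) P(X = k) · P(Y ≥ 5 − k)

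- q = 0.20, all count (p = 0.20): 0.1209 + 0.2589 = 0.380.
- q = 0.20, h = 1/4 (p = 0.20 × 0.75 = 0.15): 0.0500 + 0.1281 = 0.178.
- q = 0.10, all count (p = 0.10): 0.0128 + 0.0343 = 0.047.
- q = 0.10, h = 1/4 (p = 0.075): 0.0046 + 0.0115 = 0.016.

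The values of q and h are assumptions, because the documents give neither. The range is wide:

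| q | h = 0 | h = 1/4 | h = 1/2 | h = 1 |
|---|---|---|---|---|
| 0.10 | 0.047 | 0.016 | 0.003 | 0 |
| 0.20 | 0.380 | 0.178 | 0.047 | 0 |

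**Step 4: cost of counting every treatment-related death.** The prior, limit and cutoff are the same, so the boundaries are the same. If the true rate across all classes is exactly 0.10, the chance of crossing at any of the three looks is 0.0471 by 20 patients plus 0.0090 at 30, or 5.6%.

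**The case against.** The strongest reply is that few deaths would escape. No section classes a fatal infection or bleed as hematological. Table 2 covers only counts. The cited lenalidomide-rituximab study reports infection with fever (24%) separately from neutropenia. The instruction to record a diagnosis rather than signs points toward sepsis, pneumonia or haemorrhage, all of which would naturally count. This largely stands, and it makes the size of the gap uncertain. It does not close the gap: Table 5 puts grade 3 neutropenia with fever in its neutropenia row, so the protocol can be read either way.

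A reader might infer from the background that fatal marrow toxicity is the expected danger and would go uncounted. The documents do not support that. In the untreated-patient study, "they encountered severe toxicities (tumor lysis, fatal sepsis) in the first two patients enrolled", but fatal sepsis is naturally non-hematological and would already count. The five febrile neutropenia episodes after that study's amendment are not reported as fatal. Neutropenia is shown to be frequent, not to be the main cause of death.

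A reader might also infer that the grade 5 rule is the last protection against fatal toxicity. It is not. Safety monitoring covers all deaths. Serious events go to the IND Office within 5 working days regardless of attribution, and unexpected, related fatal events within 24 hours. Under Section 7 the investigator, the IND Office and both companies may end the study at any time. These routes make unnoticed continuation unlikely, but none is a numerical boundary, and none repairs the definition of the one the plan chose to set.

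Finally, the effect is small if few deaths are involved. At a rate of 0.20 with only 5% of deaths classed hematological, stopping by 20 falls from 0.380 to 0.337. That is a fair limit on the size.

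**Conclusion.** The point holds as a gap in the event definition. As written, a treatment-related death classed as hematological contributes to none of the toxicity rules, and the plan leaves that class undefined for them. It is not established that febrile neutropenia or thrombocytopenic bleeding deaths are excluded; that depends on coding.

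Under the assumed rates, the chance of stopping by 20 patients is roughly halved at a death rate of 0.20 with a quarter uncounted (0.38 to 0.18). At 0.10, the plan's own limit, the rule rarely fires either way (0.047 against 0.016). Both comparisons rest on assumed rates and shares and on deaths occurring independently across patients. The correction is worth making because it removes the dependence on coding and needs no change to the boundaries.

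**What to change.** In Section 10, where the grade 4 and grade 5 rules are defined, state that p(TOX5) is the probability of a treatment-related (grade 5) death of any organ class, hematological or not. Repeat the same event in the sentence that lists the boundaries.

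Keep the plan's own attribution standard, the beta(0.2, 1.8) prior, the 0.10 limit, the 0.95 cutoff and 4/10, 5/20, 7/30. Leave the grade 3 or higher and grade 4 rules, and their exclusion of cytopenia, as they are. Table 9 describes futility and the main toxicity rule only, so it does not change.

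The cost is one definition and a higher chance of stopping when some deaths are hematological. If the true rate of treatment-related death is exactly 0.10, the chance of crossing over three looks is 5.6%. The sponsor should confirm that the 0.10 limit is still the one it wants for the broader event.

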3. STUDY DESIGN DESCRIPTION OF THE STUDY

This is a single arm phase II study of Combination of Lenalidomide and Obinutuzumab in Patients with Chronic Lymphocytic Leukemia/Small Lymphocytic Lymphoma (CLL-SLL) with recurrent disease. Up to 30patients will be enrolled from M. D. Anderson Cancer Center, at a rate of 1-3patients per month. The primary efficacy endpoint is overall response and safety is one of the secondary endpoints. We will monitor futility and safety of the treatment combination using a Bayesian design by Thall, Simon and Estey, in cohort size of 10.

Response to treatment will be assessed according to NCI-WG 2008 working group criteria at 3, 6 months from the beginning of therapy and every 6 months thereafter. The investigator assessment of response and progression will be considered primary for all endpoints described in the study.

The estimated patient accrual is 1-3 per month. And the trial accrual time is estimated to be about 10-20 months. The end of study is defined as 5 years after the last patient was enrolled (unless all patients have died).

OUTCOME MEASURES

Efficacy Outcome Measures

Response will be assessed by means of clinic visits, complete blood counts, imaging if clinically indicated radiographic images as clinically indicated).

Clinic visits (this will include vital signs and physical exam) at the University of Texas, M D Anderson Cancer Center (UTMDACC) are required after 3, 6 cycles (obinutuzumab and lenalidomide) and 12 cycles (lenalidomide) and once every 6 cycles thereafter. Hematology complete blood counts (white blood cells, hemoglobin, platelets and differential) will be monitored once weekly for the first five weeks and once every two weeks in case of dose increase until a stable, dose of lenalidomide has been established for the specific patient. Blood will be drawn for routine tests.

Bone marrow biopsy and aspiration will be performed and evaluated by flow cytometry after 3, 6 cycles (obinutuzumab and lenalidomide) and after 12 cycles (lenalidomide). If patients stay on the study past 12 cycles, once every 6 cycles, they will have if clinically indicated a bone

marrow biopsy and aspirate evaluated by flow cytometry to check the status of the disease .

Safety Outcome Measures

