5. TREATMENT PLAN

This is a single arm phase II study of Combination of Lenalidomide and Obinutuzumab in Patients with Chronic Lymphocytic Leukemia/Small Lymphocytic Lymphoma (CLL-SLL) with recurrent disease.

Obinutuzumab will be given 100 mg iv d1, 900 mg iv d2 and 1000 mg d8(+/-3 days) and d15 (+/-3 days) for the first cycle, and 1000 mg d1(+/-10 days) along cycles 2-6 in a 28 days cycle. Lenalidomide will be given at 5mg per day from day 9 until day 56 and at 10 mg per/day from day 57 until progression or excessive toxicity. See Study Calendar (Appendix 2).

Patients will self-administer lenalidomide daily.

This research study protocol allows the patient to receive up to 9 infusions of Obinutuzumab .

Response will be evaluated after three, six and twelve cycles and every 6 months thereafter .

The estimated patient accrual is 3-6 per month. And the trial accrual time is estimated to be about 10-20 months. The end of study is defined as 5 years after the last patient was enrolled (unless all patients have died).

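### The grade 5 stopping criterion has boundaries only at 10, 20 and 30 patients, so toxic deaths can meet it between looks with no formal rule to act on

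*Combined protocol and SAP*

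**What the plan says.** Section 10 (Method of Analysis, after Table 9) adds separate rules for grade 4 and grade 5 non-hematological toxicity: "we will monitor the grade 4 and grade 5 non-hematological toxicities separately, throughout the study and in cohort size of 10". For grade 5, "a beta(0.2, 1.8) prior is assumed", and the trial is to stop when the posterior probability of a rate above 0.10 exceeds 0.95. The boundaries that follow are 4 of 10, 5 of 20 and 7 of 30 patients evaluated. No grade 5 boundary is given for any other number of patients.

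The same section fixes the size of the trial: "The patient sample size will be 30 patients". Table 9 gives operating characteristics for the response rule and the grade 3 or higher rule only.

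The accrual rate, which sets the time between looks, is stated twice. Section 3: "The estimated patient accrual is 1-3 per month". Section 5: "The estimated patient accrual is 3-6 per month".

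**The concern.** A batch of 10 is natural for a response that is read at 3 months. A death needs no such assessment window. With boundaries only at 10, 20 and 30, the plan's own threshold for excess toxic death can be crossed between looks while enrolment continues, and later survivors can bring the posterior back under 0.95 by the time of the look. The look at 30 cannot protect enrolment, so only two looks can.

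The wording also pulls two ways. Monitoring throughout the study suggests continuous review; cohorts of 10, with three printed boundaries, does not. If continuous review is intended, staff have no boundaries to apply. At stake is the number of patients exposed after the plan's own evidence threshold has been passed.

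**Working it through.** **Inputs (Section 10).** Prior beta(0.2, 1.8) (mean 0.10, weight of 2 patients), limit 0.10, cut 0.95, looks at 10, 20 and 30, maximum 30 patients.

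**Formula.** With x deaths in n patients, p(TOX5) follows beta(0.2 + x, 1.8 + n − x). The boundary at n is the smallest x with Pr(p > 0.10) > 0.95.

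**1. The printed boundaries reproduce.**

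| n | one death fewer | printed boundary |
|---|---|---|
| 10 | 3/10: 0.933 | 4/10: 0.987 |
| 20 | 4/20: 0.875 | 5/20: 0.959 |
| 30 | 6/30: 0.931 | 7/30: 0.976 |

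**2. The same criterion between looks.** It is met at 2/2 (0.984), 2/3 (0.967), 3/4 (0.995), 3/8 (0.962), 4/14 (0.958) and 5/21 (0.951). It is not met at 1/2 (0.815), 2/4 (0.945) or 3/9 (0.949). Boundaries for every n:

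| Patients | 2–3 | 4–8 | 9–14 | 15–21 | 22–27 | 28–30 |
|---|---|---|---|---|---|---|
| Deaths to stop | 2 | 3 | 4 | 5 | 6 | 7 |

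These contain 4/10, 5/20 and 7/30.

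**3. Dilution.** Three deaths in the first 4 patients give 0.995. If the next 6 patients survive, the first look sees 3/10 = 0.933 and does not stop. By simulation of 100,000 trials, the criterion is met before patient 10 in 5%, 24% and 48% of trials at true rates of 10%, 20% and 30%. In 4%, 13% and 15% of all trials it is met before patient 10 but no longer met at the 10-patient look.

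**4. Operating characteristics.** Exact binomial recursion: f_n(x) = (1 − p)·f_{n−1}(x) + p·f_{n−1}(x − 1), removing the mass at or above the boundary at each look. Mean deaths = p × mean enrolled. Assumptions: grade 5 rule alone, deaths known at once, patients entered one after another. A survivor cannot trigger a crossing, so reading after every patient is the same as reading at every death.

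| True rate | P(stop before 30): cohorts of 10 | at every death | Mean enrolled | Mean deaths |
|---|---|---|---|---|
| 5% | 0.3% | 1.5% | 30.0 → 29.7 | 1.5 → 1.5 |
| 10% | 4.7% | 10.9% | 29.4 → 28.0 | 2.9 → 2.8 |
| 20% | 38.0% | 56.5% | 25.0 → 20.2 | 5.0 → 4.0 |
| 30% | 76.8% | 90.4% | 18.8 → 12.3 | 5.6 → 3.7 |

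Looks every 5 patients fall between: 5.9%, 45.3% and 84.2% at true rates of 10%, 20% and 30%.

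**5. Delayed deaths.** The documents give no timing of deaths, so this is an assumed range. At a true rate of 20%, 2 patients per month, patients enrolled as denominator and no accrual hold, approximate simulated mean enrolment under cohorts of 10 versus every death is:

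- deaths spread evenly over 3 months: 27.1 versus 24.2, so 0.2 × 2.9, about 0.6 deaths saved;
- over 6 months: 28.5 versus 26.5, about 0.3 to 0.4 saved;
- over 12 months: 29.7 versus 29.1, about 0.1 saved.

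At 4.5 patients per month with deaths spread over 3 months, the saving is about 0.3.

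**6. Time between looks.** At 1–3 per month, 10/3 to 10/1 is about 3 to 10 months. At 3–6 per month, 10/6 to 10/3 is about 2 to 3 months.

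**The case against.** **Cohort monitoring is a legitimate choice.** It is applied to all four rules and the boundaries are correctly derived. That stands: there is no arithmetic error, and the point is an improvement to the design.

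**Deaths are not ignored between looks.** A reader might infer that nothing is reviewed before patient 10. The documents do not support that. The adverse event section requires a written report within 24 hours of unexpected, related, life-threatening or fatal events, and sends serious adverse events to the IND Office within 5 working days. Section 7 lets the investigator, the IND Office and the supporting companies end the study at discretion. These are real safeguards, but none is linked to the 95% criterion. The responder-based accrual pause in Section 10 does not respond to deaths. The wording "if at any time during the trial we determine that there is more than 95% chance that the toxicity rate is at least 50" per cent belongs to the grade 3 or higher rule, which does not fill the gap: 3 of 4 patients with such toxicity gives only 0.81 under its beta(1, 1) prior.

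**The introduction's lenalidomide trial is not a precedent.** Of that study it reports that "they encountered severe toxicities (tumor lysis, fatal sepsis) in the first two patients enrolled". A reader might infer that the same pattern would cross the criterion here. The text does not report two deaths, and one death in two patients gives 0.815. Neither the printed boundaries nor event-driven ones would stop the trial.

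**The gain can be small.** Lenalidomide is planned for a year, with possible extension (Section 6), so deaths may come long after entry. This stands, and the savings in step 4 are upper-end figures.

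**More looks at the same cut cost something.** Stopping at a true rate of exactly 10% rises 2.3-fold, and at 5% about five-fold from a very low base. This also stands and should be reported.

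**Conclusion.** The concern holds in this form: the grade 5 criterion has no boundary between 10, 20 and 30 patients, it can be met in those gaps, and a crossing can be lost before the next look. The printed boundaries themselves are correct.

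With immediate deaths and sequential entry, event-driven reading saves about 1 toxic death at a true rate of 20% and about 2 at 30%. The gain shrinks toward zero if deaths occur many months after entry or accrual is fast. Against that, the probability of stopping before 30 patients increases by 6.2 percentage points at the 10% limit and 1.2 points at a 5% rate. All these figures treat the grade 5 rule alone. This is a worthwhile, inexpensive change to a defensible design choice, and the wording on continuous versus cohort monitoring needs clarifying in any case.

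**What to change.** In Section 10, keep the prior, the 0.10 limit and the 0.95 cut, and evaluate the grade 5 criterion at every grade 5 event. Replace the three printed grade 5 boundaries with: stop at 2 deaths within 2–3 patients, 3 within 4–8, 4 within 9–14, 5 within 15–21, 6 within 22–27, or 7 within 28–30. Name one denominator, for example patients treated to date.

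Add operating characteristics for this rule, including the probability of stopping at true rates of 5% and 10%, and a range of assumptions on the timing of deaths. If 10.9% at the limit is judged too high, looks every 5 patients are an intermediate option (5.9% at a 10% rate, 45% at 20%).

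Reconcile the accrual rates in Sections 3 and 5, since they set the interval between looks.

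The cost is one boundary table, a short table of operating characteristics and a sentence. No patients or procedures are added.
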